## INTERVENTION PROTOCOL

From the following scheme (Scheme 3), each training session of the muscle strengthening program was structured for each of the intervention groups, which was based on the principles of training and the Earl and Hoch protocol described in the theoretical framework.

*Scheme 3: A y B Strengthening Program*

After the adjustments described in the pilot test, the strengthening program was applied to the forty patients who were previously randomized to the intervention protocols for groups A and B.

Each of the exercise sessions lasted approximately 45 to 60 minutes, of which, the first 8 to 10 minutes were dedicated to the initial warm-up exercises, the same for program A and B, which gave way to the phase central to the session, that is to say the strengthening exercises: group B took about five minutes less to complete it, because they performed an exercise less than group A in each of the three phases set out in the program; This phase of strengthening lasted approximately 20 to 30 minutes of the total session.

Each session was divided into four parts, of which the second part (central strengthening phase) included between 24 and 28 exercises in total, group A and B respectively. In addition to this, the anatomical conditioning phase was carried out in two weeks, in which 5 to 6 strengthening exercises were prescribed depending on the treatment group, but for both groups the volume was two sets of 10 repetitions, with approximately 30 seconds rest between sets and between exercises, with an execution speed of 1/1 (concentric / eccentric contraction ratio) that allowed patients to adapt to adequate movement control and therefore, joint protection.

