Later, to evaluate if there were differences between the groups of treatment after the intervention on the variables of interest, deltas were generated from the Kujala test, EVA, number of squats, Q angle, balance, physical activity and core strength. with iron and trunk extension, evaluating normality by means of graphic and numerical methods. For the analysis of the differences of medians between the groups, taking into account that the outcomes did not present a normal distribution, and assuming the assumption of independence of the variables, we proceeded to use the non-parametric Mann-Whitney U test. Finally, through the Wilcoxon test, intragroup differences were evaluated for strength, pain and physical activity components.

The hypothesis tests were presented in two tails with an alpha of 0.05 and all the analyzes were executed with the statistical program STATA version 14.0.

BASELINE:

Study population

Therapeutic Effect of Two Muscle Strengthening Programs in Patients with Patellofemoral Pain Syndrome

Table 5 describes the general characteristics of the study population at baseline. There were no significant differences between the two intervention groups (A and B), which means that the randomization was adequate; however, in the total score of the Kujala test there was a difference of 12.5 points between the groups, with a lower score for group B (53.0), which indicates better core strength for these patients. Finally, the sex variable was defined as categorical and the rest of the variables as continuous, for which the medians and their respective interquartile range (IR) are reported, taking into account that the variables did not have a normal distribution.

Table 5: Baseline variables of the study population

Variables	Treatment A (n 20) Medium (RI)	Treatment B (n 20) Medium (RI)	Value p ^a
Sex * (Male, Ref)			
Female	90 (65.7-97.6) *	90.0 (65.7-97.6) *	1,000 ^b
Age	32.5 (25.5-38.0)	29.0 (25.0-36.5)	0,569
Initial weight (Kg)	64.6 (55.3-72.4)	62.7 (52.9-68.5)	0.379
Size (cm)	160 (156.5-167.0)	159.5 (154.0-163.0)	0.423
IMC	25.4 (21.5-27.9)	23.8 (22.3-25.2)	0.456
% of fat	35.4 (28.9-40.4)	35.4 (24.5-38.7)	0,714
% muscle	26.9 (24.5-28.9)	26.2 (24.6-29.0)	0.849
Visceral fat	6 (3.5-7.09)	5 (4.0-6.0)	0.433
IPAQ (minutes)	3003 (1116-4638)	1617 (944-6138)	0,588
Pain	7.5 (5.5-9.0)	7.0 (5.5-8.5)	0.764
Kujala total score	65.5 (42.5-72.5)	53.0 (44.5-71.5)	0,892
Q angle			
Straight	19.0 (15.0-20.0)	18.0 (15.0-20.0)	0,557

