Kujala total test score	65.5 (42.5-72.5)	88.0 (81.0-95.0)	23.0 (16.0-37.0)	53.0 (44.5-71.5)	78.0 (64.0-88.0)	17.0 (8.0-24.0)	0.025
Squats	10.0 (8.0-18.5)	35.0 (30.0-38.0)	20.0 (18.0-25.0)	12.5 (8.5-20.0)	35.0 (29.0-38.0)	20.0 (15.0-24.0)	0.670
IPAQ (minutes)	3003 (1116-4638)	4275 (2587-6522)	1539 (807-2457)	1617 (944-6138)	4598 (2888-7344)	1977 (1191-2815)	0,492
Q angle							
Straight	19.0 (15.0-20.0)	18.0 (15.0-20.0)	0 (-2; 2)	18.0 (15.0-20.0)	18.0 (15.0-20.0)	0 (-2; 2)	0.819
Left	18.0 (15.0-20.0)	18.0 (16.0-20.0)	0 (-2; 2)	18.0 (15.0-20.0)	18.0 (15.0-20.0)	0 (-2; 2)	0.672

Balance with open eyes							
Straight	30.0 818.25- 45.0)	45.0 (45.0- 45.0)	11.5 (0- 25.5)	40.0 (18.25- 45.0)	45.0 (45.0- 45.0)	7.5 (0- 30.0)	0.916
Left	29.5 (15.75- 44.0)	45.0 (45.0- 45.0)	9.5 (0- 21.5)	25.75 (14.5- 45.0)	45.0 (45.0- 45.0)	20.0 (0- 30.0)	0.282
Balance with closed eyes							
Straight	4.5 (3.0- 9.259)	28.5 (21.0- 35.0)	20.0 (14.0- 27.5)	5.25 (3.0- 7.25)	23.5 (16.5- 31.5)	19.0 (9.5- 24.0)	0.671
Left	5.0 (3.0- 8.7)	30.0 (23.5- 38.0)	24.5 (13.0- 30.5)	4.25 (3.5- 7.259)	27.5 (14.0- 34.5)	20.0 (10.5- 30.5)	0.349
Griddle	20.5 (12.0- 32.0)	60.0 (45.0- 70.0)	37.0 (24.0- 48.0)	30.0 (13.5- 33.5)	35.0 (20.0- 60.0)	10.0 (2.0- 15.0)	<0.001
The t. Right	15.0 (10.0- 21.0)	45.0 (38.0- 51.0)	30.0 (19.0- 36.0)	15.0 (9.5- 20.0)	22.0 (16.0- 38.0)	6.0 (2.0- 12.0)	<0.001
The t. Left	12.5 (10.5- 19.0)	45.0 (36.0- 56.0)	30.0 (17.0- 40.0)	18.0 (11.0- 23.0)	21.0 (15.0- 34.0)	5.0 (-2 - 10.0)	<0.001
Trunk extension	13.5 (6.0- 26.5)	61.0 (50.0- 75.0)	49.0 (30.0- 55.0)	13.5 (2.5- 20.0)	30.0 (15.0- 60.0)	15.0 (7.0- 34.0)	0.001

* U of Mann-Whitney for the delta of the measurements between the groups.

He was also interested in this research, to observe the intra-group differences of including hip and knee muscle strengthening exercises (conventional physiotherapeutic treatment) performed in the same way for both intervention groups, as mentioned in the description of the strengthening protocol.

Intragroup differences

Therapeutic Effect of Two Muscle Strengthening Programs in Patients with Patellofemoral Pain Syndrome

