In **Table 9**, differences in medians and interquartile ranges their entire study population at the beginning and end of treatment for muscle strength, pain and level of physical activity is. It can be seen that the gluteal and quadriceps muscle strength measured with the squat test at the end of the treatment was the same in both groups, with a statistically significant p value (<0.001), which means that the whole population increased strength in a significant way.

In the same way, a similar effect was observed in the median pain measured with the VAS at the end of the treatment, because they all reported a decrease in pain, this difference being statistically significant, with a p-value less than 0.001. However, in the measurement of physical activity level with the long IPAQ at the end of the treatment, it was observed that the study population in group B spent less time practicing physical activity at the beginning of treatment, but both groups increased in time similar this practice at the end of the treatment; however, this difference was not statistically significant.

Table 9: Difference of intragroup medians for muscle strength, pain and physical activity level.

Variable	Treatment A			Treatment B		
	Initial Medium (RI)	Final Medium (RI)	Value p *	Initial Medium (RI)	Final Medium (RI)	Value p *
Squats	10.0 (8.0-18.5)	35.0 (30.0-38.0)	<0.001	12.5 (8.5-20.0)	35.0 (29.0-38.0)	<0.001
IPAQ (minutes)	3003 (1116-4638)	4275 (2587-6522)	0.029	1617 (944-6138)	4598 (2888-7344)	0.012
Pain (EVA)	7.5 (5.5-9.0)	2.0 (0.0-2.0)	<0.001	7.0 (5.5-8.5)	2.0 (0-4)	<0.001

* Wilcoxon nonparametric test

Muscular Strength and Static Balance

In **Table 10**, the correlation between the muscle and gluteus muscle strength differences measured with the squat and unipodal balance test evaluated with the One Leg Stance test with open and closed eyes by treatment groups is shown, with which it is emphasized that, for both treatment groups, the unipodal balance improved clinically significant. However, for the study group (A), this correlation was greater (strong), especially in the variable with open eyes for both lower limbs, indicating that by increasing muscle strength (glutes and quadriceps in this case) it is improved the unipodal balance. Although there is an increase in the balance for both treatment groups, there is a stronger correlation when core exercises are included, which is what happens in group A.

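### Groups are compared only on unadjusted change scores: valid under randomisation, but less precise than a baseline-adjusted comparison, which matters most for pain (p = 0.058)

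*SAP*

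**What the plan says.** Under Bivariate Analysis, the SAP forms a before-after difference for each outcome: "deltas were generated from the Kujala test, EVA, number of squats, Q angle, balance, physical activity and core strength". For the comparison between groups, "we proceeded to use the non-parametric Mann-Whitney U test". The Table 8 footnote confirms what was tested: "U of Mann-Whitney for the delta of the measurements between the groups". On error level, "The hypothesis tests were presented in two tails with an alpha of 0.05".

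The Protocol states that the programme was "applied to the forty patients who were previously randomized", and SAP Table 5 shows 20 patients in each group. The supplied text contains no covariate-adjusted comparison. Table 8 gives initial, final and delta values for every outcome, so the data for an adjusted analysis already exist.

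**The concern.** A change score subtracts the whole baseline value, which fixes the slope of final on baseline at 1. When the true slope is below 1, this over-corrects and adds noise. Adjusting for baseline as a covariate lets the data set the slope, and in large samples its variance is no greater than that of the change score. The gain does not depend on any observed imbalance.

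With 20 patients per arm, the gain is worth having. Pain is the outcome where it matters most. The between-group p value is 0.058, the text under Post-Intervention Results calls the difference non-significant but clinically relevant, and the closing paragraph still concludes that adding core exercises reduces pain more. Median deltas differ (-6 v -4) while final medians are equal (2 v 2), so how baseline is handled affects how the result reads.

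There is also a problem of interpretation. Where a scale has a floor or ceiling that many patients reach, the size of the change is partly set by where the patient started.

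**Working it through.** **Inputs.** Medians, quartiles and p values come from SAP Tables 5 and 8. The documents give no baseline-final correlation r, so r = 0.3, 0.5 and 0.7 are assumed.

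**The SAP's own figure.** The baseline Kujala gap is 65.5 - 53.0 = 12.5, as the text states.

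**1. Precision.** Take the variance as 1 at both times. The variance of change is 2(1 - r), and the variance after adjustment is 1 - r². The ratio is (1 + r)/2.

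| r | 2(1 - r) | 1 - r² | Ratio | 40 × ratio | √ratio (CI width) |
|---|---|---|---|---|---|
| 0.3 | 1.40 | 0.91 | 0.65 | 26 | 0.81 |
| 0.5 | 1.00 | 0.75 | 0.75 | 30 | 0.87 |
| 0.7 | 0.60 | 0.51 | 0.85 | 34 | 0.92 |

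So 26, 30 or 34 patients analysed with adjustment would give the precision of 40 analysed by change. The formula is for linear ANCOVA against a mean change. It is only a guide to rank ANCOVA against Mann-Whitney.

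**2. Is equal variance plausible?** Not for several outcomes. In arm A the Kujala interquartile width goes from 72.5 - 42.5 = 30 to 95 - 81 = 14, and the pain width from 9.0 - 5.5 = 3.5 to 2 - 0 = 2.

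A rough back-calculation treats widths as proportional to SDs: r = (w0² + w1² - wd²)/(2·w0·w1), where w0, w1 and wd are the baseline, final and delta widths.
- Kujala A: (900 + 196 - 441)/840 = 0.78.
- Kujala B: (729 + 576 - 256)/1296 = 0.81.
- Kujala pooled slope: (327.5 + 524.5)/(900 + 729) = 0.52.
- Kujala variance ratio: (196 + 576 - 852²/1629)/(441 + 256) = 326/697 = 0.47.
- IPAQ, same method: slope about 0.88, variance ratio about 0.90.
- Pain A: (12.25 + 4 - 36)/14 = -1.41, which is impossible. The method therefore says nothing about pain. It also fails for prone plank in B (1.14).

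**3. How far apart were the arms at baseline?** For 20 v 20, the SD of U is √(20·20·41/12) = 36.97. A two-sided p value with normal deviate z puts P(A > B) at a distance z·36.97/400 from 0.5.
- Kujala: quartiles 42.5-72.5 v 44.5-71.5, p = 0.892, z = 0.136, distance 0.013.
- IPAQ: quartiles 1116-4638 v 944-6138, p = 0.588, z = 0.542, distance 0.050.

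**4. How would adjustment move the estimate?** The adjusted effect minus the change-score effect is (1 - b) × (baseline A - baseline B), where b is the slope. Assume b = 0.7 to 0.3.
- Kujala, median gap 12.5: 0.3 × 12.5 = 3.8 to 0.7 × 12.5 = 8.8 points towards A.
- Kujala, approximate means (quartiles and median averaged) 60.2 v 56.3, gap 3.8: 1.1 to 2.7 points towards A.
- Pain, median gap 7.5 - 7.0 = 0.5: 0.15 to 0.35 points against A, beside a median delta gap of -6 - (-4) = -2.

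**5. Bounded scales.** Open-eyes balance ends at 45.0 (45.0-45.0) in both arms on both sides.
- Right: A starts lower (30.0 v 40.0) and has the larger delta (11.5 v 7.5; p = 0.916).
- Left: B starts lower (25.75 v 29.5) and has the larger delta (20.0 v 9.5; p = 0.282).

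Neither contrast is significant, but on each side the larger delta belongs to the arm that started lower.

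**The case against.** The strongest reply is that nothing here is invalid. Under randomisation, Mann-Whitney on deltas is a legitimate test, and a delta does use the baseline; what is missing is covariate adjustment. That stands, so the point is about efficiency and interpretation.

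A reader who sees the Table 5 medians (Kujala 65.5 v 53.0, IPAQ 3003 v 1617) might infer more. The documents do not support these inferences:
- **The arms started materially apart.** The gaps are in the medians. Quartiles overlap closely for Kujala and widely for IPAQ, and the rank overlap in step 3 is nearly complete for Kujala. A non-significant baseline test does not prove balance, but the medians alone do not show imbalance.
- **Regression to the mean drives the contrast.** In expectation it acts on both arms alike, and only chance imbalance carries over. For Kujala it would favour B, the arm with the lower median, so it cannot explain A's larger gain (23.0 v 17.0, p = 0.025).
- **The SAP attributes the IPAQ pattern to B's lower start.** Under Intragroup differences it only remarks that "group B spent less time practicing physical activity at the beginning of treatment" and that both groups then rose similarly.

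Two further objections stand and shape the fix. The results are already reported, so promoting a new analysis above the reported one would be a post hoc switch. And adjusted final values are uninformative for open-eyes balance, where most patients tie at 45.0.

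**Conclusion.** The point holds as one of precision. The only between-group test is Mann-Whitney on unadjusted change, and a more precise comparison is available from data already collected. If variances are equal and r is 0.3 to 0.7, the adjusted variance is about 65% to 85% of the change-score variance, and the confidence interval about 19% to 8% narrower. Both conditions are assumptions. The rough figures from Table 8 (0.47 for Kujala, 0.90 for IPAQ) fall outside that range, so the size varies by outcome and cannot be fixed without patient-level data.

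It should not be inferred that adjustment would make pain significant. The estimate might shift slightly against A while its variance falls, and the documents do not show which would prevail. No reported conclusion is shown to be reversed. The pain claim simply rests on a borderline result from a less efficient test.

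**What to change.** Add a between-group comparison of final values adjusted for their own baseline, for example by rank-based ANCOVA. Do this first for pain and the Kujala total, then for the other Table 8 outcomes not at ceiling. Because a rank analysis gives no effect in the units of the scale, also report an estimate with its 95% CI from a baseline-adjusted model. State the number of patients analysed in each arm at follow-up.

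Label this as an analysis added after the results were known, and report it beside the existing Mann-Whitney on deltas, not in its place. For open-eyes balance, say that both arms finish at 45.0 and that the deltas therefore largely reflect starting values.

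The cost is a little more analysis work on existing data.

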The warm-up included 13 exercises, performed in an average time of 8 to 10 minutes and in the same way during the eight weeks of intervention, while, in the fourth part of the session, final stretching or return to calm, the participants performed 8 exercises during the first 6 weeks of intervention and 10 exercises in the last two weeks. Each exercise was performed for 30 seconds, which took approximately 8 to 10 minutes to complete them. Finally, the neuromuscular component (static balance training with one-foot balance exercises) was performed after muscle strengthening exercises. It was based on 8 exercises, which changed every two weeks with a duration between 30 to 45 seconds each, and between one to two repetitions per exercise depending on the week of intervention. The three phases mentioned above were exactly the same for both treatment groups.

All participants participated in groups of four people per session, three exercise sessions per week for eight weeks in total, at the IPS-CAFAM (Institución Prestadora de Salud de la Caja de Compensación Familiar) Rehabilitation Center, for a total of twenty-four sessions, which were supervised by a Physiotherapist, who was responsible not only to verify the quality in the performance of each of the exercises, but to teach during the first two weeks of intervention (anatomical conditioning phase) the fundamental bases of adequate breathing and feed them back during all the intervention protocol, as well as guaranteeing a correct posture in performing the training and thus avoiding the appearance of low back pain as a result of a poor training technique, as well as the increase in intra-abdominal pressure generated by the “pushing” when it is not known to breathe properly during strength training.

The hydration of each participant was also crucial during each training session. Similarly and prior to the start of the protocol, all patients were instructed and suggested the importance of wearing appropriate footwear for training (sports sneakers, sportswear - during the first two weeks they were suggested to wear shorts to observe the position of the knees during the exercises and later the use of liquefied pants up to the ankle to avoid rubbing the elastic bands with the skin-; likewise, they were instructed to bring water bottle, towel to dry the sweat and not to use elements that could injure them during the exercise, such as bracelets or necklaces.

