To evaluate the effect of muscle strength on the alignment of the knees and analyze the effect of muscle strength on the unipodal balance, **Table 8** shows the deltas of the medians (changes or differences observed after the intervention) for each of the treatment groups and for each of the variables measured at the beginning and end of the intervention.

In this way, when they include or add exercises for the strengthening of the core, to the traditional treatment of SPF or anterior knee pain, the quality of life measured with the Kujala test in these patients increases, especially by the significant reduction of pain, highlighting for example, that for the total score of the Kujala test, there was a statistically significant difference ($p = 0.025$), with an increase of 5 points for group A (group A = 23.0, group B = 17.0), which indicates that the population of the study group improved their quality of life more after the intervention compared with the people of group B. A similar effect is observed in the increase of the strength of the core musculature for group A, especially in the oblique force evaluated with the side plate, with a difference of 30 seconds for group A, and only five seconds for group B on the left lateral plate, with a statistically significant p value (<0.001).

Therapeutic Effect of Two Muscle Strengthening Programs in Patients with Patellofemoral Pain Syndrome
On the other hand, the differences for the total pain evaluated with EVA were -6 and -4 for group B, with an interquartile range (-10; -4) and (-7; -3) respectively. Although p was not statistically significant, these differences were clinically relevant. For the hip and knee muscle strength, measured with the squat test, there was no statistically significant difference in the median of the deltas between the treatment groups, but there was one in each group, which means that all of them increased strength muscle in hips and knees, as a result of strengthening for these muscle groups.

Table 8: Effect of muscle strengthening on pain, knee alignment, core, hip and knee strength and balance by treatment groups.

Variable	Treatment A			Treatment B			Value p *
	Initial Medium (RI)	Final Medium (RI)	Delta Medium (RI)	Initial Medium (RI)	Final Medium (RI)	Delta Medium (RI)	
Pain (EVA)	7.5 (5.5-9.0)	2 (0-2)	-6 (-10; -4)	7.0 (5.5-8.5)	2.0 (0-4)	-4 (-7; -3)	0.058

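### Patients trained in groups of four, but the between-arm tests treat them as independent; if the groups were stable and single-arm, the Kujala p-value of 0.025 is too small

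*SAP*

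**What the plan says.** The Protocol, under Intervention Protocol, describes delivery: "All participants participated in groups of four people per session, three exercise sessions per week for eight weeks in total", supervised by a physiotherapist who corrected technique, breathing and posture. It also says that "the strengthening program was applied to the forty patients who were previously randomized to the intervention protocols for groups A and B", so patients were allocated before group training began. In each phase the central strengthening part had one exercise fewer in B than in A and took about five minutes less. Warm-up, balance work and final stretching were identical in the two arms. About 15% of patients could do one of the three weekly sessions at home.

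The SAP, under Bivariate Analysis, tests the between-arm differences in change "assuming the assumption of independence of the variables, we proceeded to use the non-parametric Mann-Whitney U test". It adds: "The hypothesis tests were presented in two tails with an alpha of 0.05". Neither document mentions a training-group variable, an intraclass correlation (ICC), a cluster term or a sensitivity analysis for group delivery.

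Table 8 gives the median Kujala change ("group A = 23.0, group B = 17.0") with p = 0.025. Among the other patient-reported outcomes, pain has p = 0.058 and IPAQ p = 0.492. The plank, side-plank and trunk-extension times have p = 0.001 or smaller.

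**The concern.** Four people who share sessions, feedback and pace for eight weeks may finish more alike than four people chosen at random from their arm. Individual randomization does not prevent this, because the correlation arises after allocation. If each group belongs wholly to one arm, the between-arm comparison carries the group-to-group variation, and a test that counts patients as independent understates its standard error. The SAP asserts independence although the protocol describes delivery that could violate it.

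What is at stake is narrow but important. The SAP's closing paragraph says that adding core exercises is more effective for pain and quality of life. Kujala is the only patient-reported outcome with a significant between-arm difference, and 0.025 leaves limited room before 0.05.

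**Working it through.** **Inputs.** Group size 4 and 40 patients randomized (Protocol, Intervention Protocol); 20 per arm (SAP, Table 5); two-sided alpha 0.05 (SAP, Bivariate Analysis); Kujala p = 0.025 and trunk-extension p = 0.001 (SAP, Table 8). The ICC is not given, so it is assumed over 0 to 0.20. Single-arm groups are also an assumption; they would give 20/4 = 5 groups per arm, ten in all. Table 8 gives no post-intervention n, so 20 per arm is carried forward.

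**The plan's own figure.** An exact Mann-Whitney p needs patient-level data. A rough check from the Table 8 quartiles of Kujala change:
- SD = IQR/1.349: A (37 − 16)/1.349 = 15.6; B (24 − 8)/1.349 = 11.9.
- Mean = (Q1 + median + Q3)/3: A 25.3; B 16.3; difference 9.0.
- SE = √(15.6²/20 + 11.9²/20) = 4.38; z = 9.0/4.38 = 2.06; p = 0.040.

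This is the same order as 0.025 but does not reproduce it, so 0.025 is taken as given.

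**Fixed, single-arm groups.** The z for two-sided p = 0.025 is 2.241. Design effect = 1 + (4 − 1) × ICC, and adjusted z = 2.241/√(design effect). The type I error columns come from simulating the unadjusted Mann-Whitney test at nominal 0.05, with 100,000 runs per ICC. The single-arm column has five groups of four per arm; the mixed column has ten groups, each with two A and two B patients.

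| ICC (assumed) | Design effect | z | p, normal | p, t with 8 df | Type I, single-arm | Type I, evenly mixed |
|---|---|---|---|---|---|---|
| 0 | 1.00 | 2.241 | 0.025 | 0.055 | 0.049 | 0.050 |
| 0.05 | 1.15 | 2.090 | 0.037 | 0.070 | 0.066 | 0.044 |
| 0.10 | 1.30 | 1.966 | 0.049 | 0.085 | 0.083 | 0.039 |
| 0.15 | 1.45 | 1.861 | 0.063 | 0.100 | 0.100 | 0.035 |
| 0.20 | 1.60 | 1.772 | 0.076 | 0.114 | 0.118 | 0.031 |

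The normal column shows the design effect alone. It crosses 0.05 when the design effect is (2.241/1.960)² = 1.308, that is ICC = 0.308/3 = 0.103, an effective sample size of 40/1.308 = 30.6.

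The t column adds the cost of estimating between-group variation from ten groups in two arms (10 − 2 = 8 df). The two columns answer different questions and should be read separately.

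**Evenly mixed groups.** The shared group effect cancels from the between-arm comparison, so its variance is roughly (1 − ICC) times what the test assumes. The direction reverses, as the last column shows.

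**Stronger results.** For p = 0.001, z = 3.291. At ICC 0.20, 3.291/√1.60 = 2.60, giving p = 0.009 (normal) or 0.032 (8 df). By design effect alone, the ICC would have to reach ((3.291/1.960)² − 1)/3 = 0.61 to pass 0.05.

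**The case against.** The strongest objection is that the premise is inferred. The protocol says "All participants participated in groups of four people per session" and no more: it does not say that membership was fixed, or that a group held one arm only. Three of the four parts of the session were common to both arms, and the arms differed by one exercise per phase, so mixed sessions cannot be excluded. This stands, and it is why both the conclusion and its direction are conditional.

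Some features may weaken any correlation. The protocol describes supervision by a physiotherapist and no group-specific instructor; if one person covered all groups, an instructor effect would not separate them. About 15% of patients (some 6 of 40) trained partly at home. These points argue for a smaller ICC but do not show that it is zero.

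A reader might infer that the Kujala result is non-significant whatever the correlation, because the 8 df column gives 0.055 at ICC 0. The documents do not support that. At ICC 0 patients are independent and the Mann-Whitney test is valid (simulated error 0.049); the 0.055 reflects only a more cautious reference distribution. Nor is it supported that slight correlation overturns the result: by design effect alone it stays below 0.05 up to an ICC of about 0.10, and the documents give no ICC.

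**Conclusion.** The gap is real: delivery was in groups, independence is asserted, and the training group is absent from the analysis. If the groups were stable and single-arm, any positive ICC makes 0.025 too small, so the significance of the Kujala difference is overstated. The size depends on the assumed ICC: p is 0.037 to 0.076 over ICC 0.05 to 0.20 by design effect, with a further penalty for having about ten groups. If the groups were evenly mixed, the reported p-value errs the other way. If membership rotated, neither simple model applies.

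The consequence is confined to the borderline Kujala result. Pain is already above 0.05 under the unadjusted test, and the core-strength differences remain significant over the range examined. The documents do not show that the Kujala finding is wrong; they leave it without the check that group delivery calls for.

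**What to change.** 1. Add a training-group identifier to the dataset, and state whether groups were fixed over the eight weeks and whether each held one arm only.
2. Report a sensitivity analysis for Kujala and pain that respects the groups, with the estimated ICC:
   - Fixed, single-arm groups: permute arm over groups, or fit a training-group random effect with small-sample degrees of freedom. With five groups per arm there are C(10,5) = 252 allocations, and the smallest two-sided p is 2/252 = 0.008.
   - Mixed groups: stratify by training group, or include a group random effect.
   - Rotating membership: say so, and qualify the independence assumption in the SAP.
3. Describe the Kujala difference in the light of that analysis.

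The cost is one extra analysis and the recovery of group membership. The documents do not mention attendance records, so their availability is an assumption; if membership cannot be recovered, the design-effect range above can be reported as a stated limitation. The downside is that the Kujala p-value may be less favourable, and a test on about ten groups has few units and limited power.
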